#### Summary of procedures during Joslin Visit 2:

Approved by  
JDC/CHS 

- Laboratory studies
- Subcutaneous adipose tissue biopsy

Testing Visit 3. To determine aerobic capacity, a standard VO2 peak test will be performed. The procedure is described in detail below. [REDACTED] or a covering study physician, will be present as the study physician. A ramp style protocol on the cycle ergometer will be used. Blood pressure and ECG tracing will be monitored and testing will terminate based on ACSM criteria (7). Blood will be obtained 15 min before, right after the exercise test and after 30 mins of rest, to measure novel adipokine responses to a maximal exercise bout. Lactate measurements will be obtained at baseline and at VO2 peak by performing either a finger stick or an earlobe stick to obtain a small drop of blood for testing. Blood samples will either be sent directly to the lab for further analysis of the specified laboratory tests or will be further processed for storage. Participants will be shown the exercise facilities and may use the exercise facilities during visit 3 if desired. Joslin Visit 3 will count as the first day of the 10 week exercise program. In anticipation of the start of the exercise training program, a wearable activity tracker and a heart rate monitor will be provided to the participants. Participants will sign for receipt of the activity tracker and the heart rate monitor. They will be taught how to use this device. An online account will be set-up in order to track activity remotely. The study coordinator, co-investigators and PI, and the participant have access to the data. After completion of the study, participants will return the activity tracker.

Summary of procedures during Joslin Visit 3:

- VO2 peak testing
- Laboratory studies
- Exercise program instruction
- Wearable activity tracker and heart rate monitor instructions

Testing Visit 3b:

For the enrolled subjects with type 2 diabetes, we are interested in the effects of an exercise bout on reductions in blood glucose. For this group of subjects, we ask subjects to perform a 45min aerobic exercise session, prior to starting the exercise training protocol.

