For testing visit 3b, subjects will be given a standardized drink to be taken at home at 7AM, and report to the CRC around 10AM. Subjects can start the visit with a finger stick blood glucose between 100-200mg/dl. An IV catheter will be placed and baseline plasma and serum samples will be collected. Subjects will exercise on the treadmill for 45 mins at approximately 75% of VO2peak as determined during Visit 3. For the determination of blood glucose, the YSI machine will be used. Blood samples will be collected through an IV catheter at baseline, 15 min into exercise, at the end of exercise, and 15, 30, 45, 60 and 75 min after exercise completion, since the vast majority of the decrease in blood glucose is seen within the first 2hr after exercise [3]. The study visits will be concluded after the last blood sample is taken. Blood glucose will be measured at the indicated time points. Hypoglycemia will be treated per established protocols if blood glucose decreases <70mg/dl. If a subject reports hypoglycemic symptoms, blood glucose will directly be measured.

Testing Visit 4. During week 5, subjects in groups 1-3 will undergo a submaximal exercise bout for 45 min at the heart rate target corresponding to approximately 75% of VO2peak. Blood draws will be obtained before, immediately after, and after 30 minutes of rest post the exercise session. Participants do not need to fast for this visit, but will be given a standardized drink. Subjects in group 4 will undergo a regular HIT exercise session. Two lactate measurements will be obtained at the beginning and at the end of this visit with the same procedure as outlined under Visit 3.

Testing Visit 5. This visit will be identical to Visit 3, except it will occur during week 10 of training.

Approved by  
JDC/CHS 

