Subjects with type 2 diabetes will monitor blood glucose 3-4 times per day and asked to report hypoglycemia in order to adjust anti-hyperglycemic medication. Subjects with type 2 diabetes will have a medical visit with the study physician at 3, 6 and at 10 weeks where dose adjustments to the subject's diabetes regimen can be made as needed. Participants will be reimbursed for parking if they decide to exercise at Joslin, up to four times per week. Participants will be instructed to log their physical activity on their wearable activity trackers and exercise logs will be monitored remotely. Participants may be contacted by phone or email for encouragement if a decrease in activity is noted. The staff at Joslin Diabetes Center is highly trained to work with type 2 diabetes patients who are sedentary. Our exercise physiologists have overseen successful exercise and weight loss programs such as Why WAIT, YOU-Turn, Do-It and LookAHEAD.

During sessions at the Joslin Diabetes Center, blood glucose measures will be taken to prevent hypoglycemia. Prior to each exercise session, participants with type 2 diabetes will be asked to check their blood sugar with a finger stick to ensure that it is at a safe level for exercise. For patients on insulin or insulin combined with oral medications, blood glucose must be at least 120 mg/dL before beginning exercise. For patients on oral medications alone, blood glucose must be at least 90 mg/dL before beginning exercise. Patients will be given juice and a snack to help raise blood glucose if it is below the required value, and study staff will re-check patients' blood sugar every 15 minutes until it is above the required value. The exercise physiologist will also explain 1) ways to gauge appropriate exercise intensity, 2) the importance of hydration, and 3) the need to report symptoms of hypotension to their clinician or study physician. During exercise, participants will rate exercise intensity using Borg Ratings of Perceived Exertion.

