Prior to VO2 peak testing, participants who have type 2 diabetes will be asked to check their blood glucose with a finger stick to ensure that it is at a safe level for exercise. For type 2 diabetes participants on basal insulin or insulin combined with oral medications, blood glucose must be at least 130 mg/dL before beginning exercise. For participants on oral medications alone, blood glucose must be at least 100 mg/dL before beginning exercise. These criteria have been used in Why WAIT and are more conservative than those recommended by the American College of Sports Medicine (9). Participants will be given juice and a snack to help raise blood glucose if it is below the required value, and study staff will re-check participants' blood sugar every 15 minutes until it is above the required value.

We will utilize a cycle ramp style protocol, which has been used extensively in at-risk populations. The procedure involves monitoring inhaled and exhaled oxygen concentration using a face mask while steadily increasing speed and grade on a treadmill every 2 minutes (see Appendix for modified Bruce protocol). The modified Bruce protocol is identical to the Bruce protocol but it starts at a lower intensity and increases intensity more gradually, so it is better suited for sedentary individuals. VO2 testing will terminate upon volitional exhaustion or if any of the criteria described in the American College of Sports Medicine's (9) indications for stopping an exercise test are met, including the following:

- 1) drop in blood pressure of  $\geq 10$  mmHg from baseline blood pressure despite an increase in workload, when accompanied by other evidence of ischemia;
- 2) moderate to severe angina;
- 3) increasing nervous system symptoms (e.g. ataxia, dizziness, or near syncope);
- 4) signs of poor perfusion (cyanosis or pallor);
- 5) technical difficulties monitoring the ECG or systolic blood pressure;
- 6) subject's desire to stop;
- 7) sustained ventricular tachycardia;
- 8) ST elevation ( $\geq 1.0$  mm) in leads without diagnostic Q-waves (other than V1 or aVR).

Approved by  
JDC/CHS 

Upon completion of the test, participants will be seated and ECG, heart rate, and blood pressure measurements will continue every 1 to 2 minutes every 5 minutes or until exercise-induced changes return to baseline.

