**Exclusion Criteria:** Potential participants will be excluded for the following criteria: Ages  $< 25$  and  $> 55$ ; HbA1c  $\leq 6.5 \pm 0.1\%$  and  $\geq 9 \pm 0.1\%$  for participants with type 2 diabetes (to maximize safety) and  $> 5.7 \pm 0.1\%$  for overweight or obese participants without diabetes; current smoking status, type 1 diabetes, heart or lung disease; acute systemic infection accompanied by fever, body aches, or swollen lymph glands; current dieting or weight loss efforts; current pregnancy; known history of HIV/AIDS; cancer; biochemical evidence of renal or hepatic dysfunction; End-Stage Renal Disease and any renal disease, defined as a creatinine above the normal limit; liver disease; demyelinating diseases such as multiple sclerosis or amyotrophic lateral sclerosis; recent blood donation; clinical history of stroke; severe hypertension (systolic  $> 160 \text{ mmHg}$  or diastolic  $> 90 \text{ mmHg}$ ); type 1 diabetes; history of keloid formation, and inability to exercise at 50% of predicted heart rate (HR) reserve at baseline. Participants taking beta-blockers, thiazolidinedione, and a basal-bolus insulin regimen will be excluded as well. Participants will also be excluded if during Joslin Visit 1, participants without established type 2 diabetes reach a glucose value of 140mg/dl or higher at the 2 hour point during the oral glucose tolerance test.

Either a current pregnancy or breastfeeding are exclusion criteria for this study, in particular for scientific reasons, since pregnancy and breastfeeding may affect myokine and adipokine secretion and interfere with the ability to exercise. To confirm that a female subject is not pregnant prior to participating in the study, a urine pregnancy test will be performed at Joslin Visit 1. Pregnancy tests will be repeated prior to performing any DXA body composition analysis for female participants if greater than 10 days have passed since prior testing. If a positive result is found, this assessment will not be performed. Participants will also be asked to use contraception during the remainder of the study.

Participants who screen positive for The American Heart Association's contraindications to exercise testing (10) (see Appendix) during pre-enrollment screening by the study physician or their clinician are ineligible for this study.

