## 6. POSSIBLE RISKS:

**Risks Associated with Exercise:** There are risks associated with the exercise intervention. Although all participants will be carefully screened and cleared for exercise, there is still a remote possibility of adverse events such as abnormal blood pressure, fainting, dizziness, arrhythmia, and in very rare instances heart attack or stroke. There also exists the risk of bodily injury including injuries to muscles, ligaments, tendons, and joints. To minimize the risk of an adverse event, all participants will be pre-screened by a physician prior to participation. All participants must be cleared for exercise before they begin the intervention. Further, an assessment of physical fitness will be performed upon study enrollment, and the exercise intervention will be tailored to each participant's fitness level. Participants will exercise to percentages of heart rate reserve that are proven to be safe. In case of an emergency, arrangements for further emergent care will be made. Another risk associated with exercise is the risk of hypoglycemia. During sessions at the Joslin Diabetes Center, blood glucose measurements will be taken to prevent hypoglycemia. Prior to each exercise session, participants will be asked to check their blood sugar with a finger stick to ensure that it is at a safe level for exercise. For patients on insulin or insulin combined with oral medications, blood glucose must be at least 110 mg/dL before beginning exercise. For patients on oral medications alone, blood glucose must be at least 90 mg/dL before beginning exercise. For the VO2peak testing, higher blood glucose targets of 130 mg/dl and 110mg/dl respectively will be used. Patients will be given juice and a snack to help raise blood glucose if it is below the required value, and study staff will re-check patients' blood sugar every 15 minutes until it is above the required value.

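### Visit 3b sets no medication-specific glucose floor for its exercise bout, and the floors stated elsewhere in the protocol conflict (120 against 110 mg/dL for insulin users)

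*Combined protocol and SAP*

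**What the plan says.** Section 2, Testing Visit 3b, applies to the type 2 diabetes group only: "we ask subjects to perform a 45min aerobic exercise session, prior to starting the exercise training protocol". The entry criterion is "Subjects can start the visit with a finger stick blood glucose between 100-200mg/dl", the same for every medication. After catheter placement and baseline sampling, "Subjects will exercise on the treadmill for 45 mins at approximately 75% of" VO2peak. Glucose is sampled at 15 minutes, at the end of exercise and five times afterwards, and is checked at once if symptoms are reported. "Hypoglycemia will be treated per established protocols if blood glucose decreases <70mg/dl".

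Three other places set floors by medication:

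- **Section 2, MIT Exercise Training Program**, for each exercise session: "For patients on insulin or insulin combined with oral medications, blood glucose must be at least 120 mg/dL before beginning exercise". The oral-only floor is 90 mg/dL.
- **Section 6, Possible Risks**, also for each exercise session: "For patients on insulin or insulin combined with oral medications, blood glucose must be at least 110 mg/dL before beginning exercise". The oral-only floor is again 90 mg/dL. For VO2peak testing this section gives 130 mg/dL (insulin) and 110 mg/dL (oral only).
- **Section 2, VO2 Peak Testing**: "For type 2 diabetes participants on basal insulin or insulin combined with oral medications, blood glucose must be at least 130 mg/dL". The oral-only floor is 100 mg/dL.

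In all three, a participant below the floor receives juice and a snack and is rechecked every 15 minutes.

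Insulin users can be enrolled. Section 3 says "Participants taking beta-blockers, thiazolidinedione, and a basal-bolus insulin regimen will be excluded as well", which leaves basal insulin permitted, and the VO2peak rule names basal-insulin users explicitly.

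**The concern.** Visit 3b is a demanding bout for a sedentary person. Under the MIT program, training starts at 20-30 minutes and about 40-50% of VO2peak, and only by week 4 aims for 45-60 minutes at about 70-75%. Visit 3b comes before any of that, at 45 minutes and about 75%. Yet its stated glucose criterion is lower than either insulin-user floor for ordinary sessions, and staff are not told whether those floors also apply.

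There are two stakes. The first is safety: an insulin user might begin exercise at a glucose level at which the protocol would elsewhere hold them back. The second is measurement. The visit exists to observe how far a bout lowers glucose, and the standing remedy for a low pre-exercise value is to feed the participant. Staff who follow the session rule would be changing the quantity under study, and staff who do not would be using a lower threshold.

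**Working it through.** The check is a side-by-side comparison. The plan reports no figure here to reproduce.

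**Minimum glucose by place (mg/dL)**

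| Place | Event | Insulin users | Oral only |
|---|---|---|---|
| Testing Visit 3b | Start of visit | 100 | 100 |
| MIT Exercise Training Program | Each exercise session | 120 | 90 |
| Possible Risks | Each exercise session | 110 | 90 |
| VO2 Peak Testing | VO2peak test | 130 | 100 |
| Possible Risks | VO2peak test | 130 | 110 |

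**Gap = floor elsewhere − 100**

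- Insulin, exercise sessions: 110 − 100 = 10; 120 − 100 = 20.
- Oral only, exercise sessions: 90 − 100 = −10, so the Visit 3b minimum is already 10 above the floor.
- VO2peak test, for reference only: insulin 130 − 100 = 30; oral only 100 − 100 = 0 or 110 − 100 = 10.

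**What this means for an insulin user at Visit 3b**

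- 100-109 mg/dL: admitted to the visit, but below both session floors.
- 110-119 mg/dL: admitted, meets the Possible Risks floor, fails the MIT program floor.
- 120-200 mg/dL: meets both.

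**Conflicts within the protocol**

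- Insulin users, same kind of session: 120 − 110 = 10.
- Oral-only participants, VO2peak test: 110 − 100 = 10.

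**Two readings of Visit 3b**

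1. The session floors do not apply. Insulin users at 100-109 mg/dL may exercise below both floors.
2. The session floors apply. An insulin user at 100-119 mg/dL (MIT program) or 100-109 mg/dL (Possible Risks) is given juice and a snack before the bout, and the measured fall in glucose then includes the effect of that carbohydrate.

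Neither reading is satisfactory. The documents do not allow the probability of hypoglycaemia, or the distortion of the glucose response, to be calculated under either one.

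**The case against.** The strongest reply is that the 100-200 mg/dL range governs starting the visit, not starting exercise. The floors elsewhere are checked before each exercise session, and Visit 3b is itself described as an exercise session. On that view both rules operate in turn: arrive within 100-200 mg/dL, then meet the floor before the treadmill. This is a fair reading. A reader might infer that the protocol authorises insulin users to exercise at 100 mg/dL whatever their medication, and the text does not go that far. What survives is that Visit 3b does not refer to the floors, that the floors disagree, and that their remedy does not suit this visit.

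A reader might also put the shortfall at 30 mg/dL by using the 130 mg/dL floor. That floor belongs to a maximal test and is not a fair comparator for a submaximal bout, so the relevant gaps are 10 and 20.

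The safeguards are real: basal-bolus users are excluded, venous access is in place, sampling is frequent and treatment is specified. They respond to a fall rather than prevent it, and 45 − 15 = 30 minutes of exercise pass without a scheduled sample. Still, they limit the risk.

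Finally, a reader might infer that Visit 3b biases the baseline biopsy, because Subject Visits allows the pre-training order to change and Testing Visit 2 allows a repeat biopsy within 7 days. The documents do not support that. The default order puts the biopsy first, swapping Visits 2 and 3 need not place it after Visit 3b, and no acute effect on tissue is stated. The same swap would put any group's biopsy after the VO2peak test. Part of the Visit 2 text is also redacted.

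**Conclusion.** The point holds as an unclear and internally inconsistent safety threshold. On a literal reading, a basal-insulin user at 100-109 mg/dL could begin the Visit 3b bout below both ordinary session floors, by at most 10 mg/dL against one and 20 mg/dL against the other. On the alternative reading, the prescribed feeding would alter what the visit measures. The conflicts of 120 against 110 mg/dL (insulin, sessions) and 100 against 110 mg/dL (oral only, VO2peak test) stand on either reading.

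The practical size is small. At most the 10 diabetes participants are concerned, and only those on insulin for the Visit 3b floor. That number is not given and may be zero. Oral-only participants already exceed their session floor at Visit 3b. The glucose response at this visit is not among the analyses listed under Analysis of Primary Outcomes, so no primary comparison depends on it. The conclusion assumes only that basal-insulin users may enrol, as the exclusion and VO2peak wording indicate. It merits correction because the change is cheap and concerns a decision staff make at the treadmill.

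**What to change.** 1. **Testing Visit 3b:** state that participants on insulin begin the exercise only if glucose immediately beforehand is at least 120 mg/dL; otherwise the visit is rescheduled and no juice or snack is given to raise glucose for the test. Keep 100-200 mg/dL for oral-only participants.
2. **Possible Risks:** change the insulin-user floor for exercise sessions from 110 to 120 mg/dL, to match the MIT program.
3. **VO2 Peak Testing and Possible Risks:** set one oral-only floor for the VO2peak test in both places.
4. **Optional and minor:** in Subject Visits, schedule Visit 3b after the baseline biopsy and any repeat of it.

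Choosing 120 rather than 110 is a judgement: it is the more cautious of the protocol's two session values. The cost is wording and occasional rescheduling for insulin users. Visit 3b already takes a baseline sample before exercise, so no new procedure is needed. Two side effects should be accepted knowingly. Insulin users will contribute Visit 3b data only from 120 mg/dL upward. And because Visit 3 counts as the first day of the 10-week program, a rescheduled Visit 3b, or a wait of up to 7 days for a repeat biopsy under item 4, should not be allowed to shorten training.

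### Two of the four pre-exercise glucose minimums for participants with type 2 diabetes are each given two different values

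*Combined protocol and SAP*

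**What the plan says.** The protocol sets a minimum finger-stick glucose before exercise, by medication class (insulin with or without oral drugs; oral drugs alone) and by procedure (training session; VO2peak test). That makes four values, and each appears in two places.

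- **Training, Section 2, MIT Exercise Training Program.** The check applies at every session: "Prior to each exercise session, participants with type 2 diabetes will be asked to check their blood sugar with a finger stick". The minimums are: "For patients on insulin or insulin combined with oral medications, blood glucose must be at least 120 mg/dL before beginning exercise", and "For patients on oral medications alone, blood glucose must be at least 90 mg/dL before beginning exercise".
- **VO2peak test, Section 2, VO2 Peak Testing.** The minimum is 130 mg/dL for participants on insulin. For the other class: "For participants on oral medications alone, blood glucose must be at least 100 mg/dL before beginning exercise". A shortfall triggers a hold: "Participants will be given juice and a snack to help raise blood glucose if it is below the required value".
- **Both procedures, Section 6, Risks Associated with Exercise.** For training: "For patients on insulin or insulin combined with oral medications, blood glucose must be at least 110 mg/dL before beginning exercise", with 90 mg/dL for oral medication alone. For VO2peak testing: "higher blood glucose targets of 130 mg/dl and 110mg/dl respectively will be used". The hold rule follows at once: "Patients will be given juice and a snack to help raise blood glucose if it is below the required value".

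**The concern.** These are go/no-go checks whose stated purpose is to prevent hypoglycaemia. If the two sections differ, the decision to start exercise depends on which page the staff member consulted. Anyone judging the trial's risk from Section 6 also reads thresholds that differ from those in the procedures. The training check recurs: MIT participants attend the centre at least twice a week for 10 weeks. The protocol also allows centre sessions outside business hours and warns that emergency medical help there may then be less accessible, so the rule needs to be unambiguous.

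**Working it through.** No sample size, power or error rate is involved. The check is a comparison of the four values, in mg/dL.

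| Procedure and medication | Section 2 | Section 6 | Section 2 minus Section 6 |
|---|---|---|---|
| Training, insulin | 120 | 110 | +10 |
| Training, oral alone | 90 | 90 | 0 |
| VO2peak, insulin | 130 | 130 | 0 |
| VO2peak, oral alone | 100 | 110 | −10 |

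The Section 6 VO2peak pair is assigned by its word for order: it comes directly after the insulin group and then the oral-only group, so 130 belongs to insulin and 110 to oral alone. The agreement at 130 supports that reading.

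**Readings affected.** Training on insulin: at least 110 but below 120, that is 110–119 mg/dL. Section 6 clears the participant; Section 2 requires juice, a snack and 15-minute re-checks. VO2peak on oral medication alone: at least 100 but below 110, that is 100–109 mg/dL. Section 2 clears; Section 6 holds.

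**Could one slip explain both?** No. The conflicts lie in different cells and have opposite signs, so changing one number leaves the other conflict in place. Each section is also regular in itself. VO2peak minus training in Section 2 is 130 − 120 = 10 for insulin and 100 − 90 = 10 for oral alone. In Section 6 it is 130 − 110 = 20 and 110 − 90 = 20. These margins follow from the same two mismatches and are not further evidence, but they show that internal regularity cannot identify the intended values.

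**Other explanations considered.**

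- *Setting.* Both training passages concern sessions at the study centre.
- *Population.* The VO2 Peak Testing text says basal insulin where Section 6 says insulin. Basal-bolus regimens are excluded, and the insulin value for that test agrees in any case. The oral-only class is the same in both.
- *Status of the Section 6 VO2peak values.* They are called targets, but the next sentence treats them as required and attaches the hold to them.
- *Form of the text.* All three places are current, continuous prose. No redaction, broken table or amendment log is involved.
- *Precedence.* None is stated.

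**The case against.** The strongest reply is that the texts are not logically incompatible. All the figures are minimums, so a reading that meets the higher one in a cell also meets the lower one, and nothing forbids holding a participant who has passed the lower. This is correct. The accurate statement is that the sections disagree on when a hold is mandatory, so staff following one would act differently from staff following the other within the two bands.

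The reach is also small. The type 2 diabetes group is planned at 10 participants (11 per group with the allowance under Sample Size), and only its insulin-treated members meet the first conflict. Up to two MIT sessions a week may take place away from the centre, where the staff-run re-check does not operate. The second conflict can arise only at the two scheduled VO2peak tests, Visits 3 and 5, with a physician present. The four conflicting figures all lie above the 70 mg/dL level below which Visit 3b treats hypoglycaemia, and the safeguard is otherwise the same in both sections. All of this stands and limits the consequences.

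The VO2 Peak Testing text also defends its values as used in an earlier programme and more conservative than guideline recommendations. That does not resolve the difference, because the Section 6 value for oral medication alone is not the one being defended. None of these points removes the contradiction.

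**Conclusion.** The concern holds. Two of the four minimums conflict, each by 10 mg/dL and in opposite directions, with no rule of precedence. The effect is confined to the type 2 diabetes group and to readings of 110–119 mg/dL (training on insulin) and 100–109 mg/dL (VO2peak on oral medication alone). The documents give neither the number of insulin-treated participants nor how often readings fall in these bands, so no count of affected sessions or tests is claimed. No endpoint, sample size or analysis changes. It should still be corrected, because these are mandatory safety thresholds. The conclusion rests only on the protocol's text and on reading the Section 6 VO2peak pair in its stated order.

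**What to change.** The sponsor and study physician should reconcile the three places together (Section 2, MIT Exercise Training Program; Section 2, VO2 Peak Testing; Section 6, Risks Associated with Exercise), settle one value for each medication class and procedure, and repeat it identically wherever it appears. A single four-cell table to which the other places refer would prevent the values from drifting apart again. Which values are right is a clinical decision, and none is proposed here.

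As an optional check at the same time, confirm that the Visit 3b starting range of 100–200 mg/dL, which is not split by medication, is meant to stand apart from the check before each exercise session. It is not counted as a conflict, since Visit 3b precedes the training programme.

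The cost is a short text amendment, with no effect on sample size or analysis.
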